More precisely, our outcome measure will be the total difficulties score from the SDQ. This is a standard SDQ measure which is constructed from summing together responses on four of the five SDQ subscales, giving a score which ranges from 0 to 40. Following existing conventions in using the SDQ (Vaz et al., 2016), if at least three of the five items within a subscale are completed, any remaining missing scores will be replaced by the mean for that subscale. If fewer than three items are completed, no score will be computed for that subscale, and if any of the four subscales are missing, the total difficulties score will not be computed. The extent of missingness in these data, including by treatment and control arm, will be presented in the report. We will also run separate models for three components; 'internalising problems' (which combines the emotional symptoms and peer relationship problems scales, 10 items), 'externalising problems' (which combines the conduct problems and hyperactivity scales, 10 items) and the prosocial scale (5 items). This division of the scales has been shown to be more appropriate for low-risk or general population samples (Goodman et al., 2010).

Subgroup analyses

We will conduct separate analysis of the subgroup of pupils eligible for Free School Meals. Pupils eligible for FSM will be identified using the variable EVERFSM_6_P available from the NPD. This analysis will be conducted for both the primary and secondary outcome; all other subgroup and additional analyses will be conducted only for the primary outcome.

We will run analyses interacting treatment allocation with FSM status, as well as running separate models for the FSM and non-FSM subgroups. The same specification will be used as for the primary analysis. The effect size for FSM pupils will be presented on the basis of the subgroup model, as per the EEF statistical analysis guidance.

Given existing research has suggested differences in impact according to prior attainment (e.g. York and Loeb, 2018), as specified in the trial protocol, we will also conduct a separate subgroup analysis for "high" and "low" attaining pupils, based on the pre-test assessments. These groups will be defined by dividing the sample in half, based on the median score on the

⁴ Further details of the reasons for missingness will be presented in the evaluation report.

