intervention has a positive effect. This additional analysis will be carried out for both primary and secondary outcomes, and will be estimated using the eefAnalytics package available within Stata (Vallis et al., 2021). For this analysis we will adopt non-informative priors; this is to ensure that the results are in large part driven by the data, rather than on a subjective judgement regarding priors (Uwimpuhwe et al., 2020). For consistency, we will adopt the same assumptions regarding non-informative priors as used in the analysis by Uwimpuhwe et al. (2020) which uses vague Gaussian priors (N(0,106) for each of the regression parameters. The report will present the effect sizes and credible intervals estimated through the Bayesian approach; along with the posterior probability that the intervention has an effect size of at least 0.1. This follows the recommendation made by Uwimpuhwe et al. (2020) regarding a suitable threshold for assessing effectiveness of educational interventions, but is also consistent with the fact that the trial was designed with the aim of establishing a MDES of 0.1, given the previous research for the US by York and Loeb (2018), which found an impact of the programme on literacy of 0.11 standard deviations. For completeness, we will also report the probability that the intervention has an effect size of at least zero (that is, that it has a positive effect). The results from the frequentist analysis will remain the main results on which the report will focus, with the results from the Bayesian approach forming an additional exploratory analysis, to provide further insight into the sensitivity of results. Any substantive differences in the results obtained from the two approaches will be discussed in the evaluation report.

Longitudinal follow-up analyses⁵

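### The two exploratory Bayesian probabilities for SDQ total difficulties point towards harm if applied as written, because benefit on that score is a negative effect size

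*SAP*

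**What the plan says.** The relevant statements are spread over five places in the SAP.

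- **Additional analyses, v1.1 update (scope).** The Bayesian work is not confined to literacy: "This additional analysis will be carried out for both primary and secondary outcomes".
- **Additional analyses, v1.1 update (quantities).** The report is to give effect sizes, credible intervals and "the posterior probability that the intervention has an effect size of at least 0.1". A second probability is then added: "we will also report the probability that the intervention has an effect size of at least zero (that is, that it has a positive effect"). No direction is set by outcome.
- **Additional analyses, v1.1 update (purpose).** The 0.1 value is presented as a "suitable threshold for assessing effectiveness of educational interventions" and is tied to earlier research "which found an impact of the programme on literacy of 0.11 standard deviations". Both probabilities are therefore meant as probabilities of benefit.
- **Secondary outcome analysis.** "our outcome measure will be the total difficulties score from the SDQ". It is a sum of four subscales running from 0 to 40, and the components are named as symptoms, problems and hyperactivity. The model is that of the primary outcome with the SDQ score put in place of YARC.
- **Primary outcome analysis and Effect size calculation.** The treatment indicator is 1 for intervention and 0 for control. The effect size is the adjusted treatment-minus-control difference divided by a pooled measure of spread.

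RQ2 in the Introduction asks whether the programme improves social development.

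**The concern.** One pair of thresholds, both on the positive side, is set for two outcomes that run in opposite directions. A higher YARC score is better; a higher total difficulties score is worse. The SAP does not reverse-score the SDQ, change the sign of its effect size, or state which direction is beneficial for each outcome.

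At stake is the probability of effectiveness quoted for RQ2. An analyst who follows the text would give a low value when the data favour the programme on the SDQ and a high value when they do not. The Bayesian analysis was added because completed post-tests fell to around a third of the number anticipated, so readers may give these probabilities some attention.

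**Working it through.** The SAP states no posterior probability for the SDQ, so there is no figure to reproduce. The check has two steps: the sign, then an illustration of size.

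**Step 1: sign, from the SAP's own definitions**

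1. ES = (treatment mean - control mean, adjusted) / s\*. Since s\* is positive, ES takes the sign of the difference.
2. The outcome is an unreversed sum of difficulties, so fewer difficulties under intervention makes the difference, and hence ES, negative.
3. So P(ES >= 0) is the probability that difficulties did not fall, and P(ES >= 0.1) is the probability that they rose by at least 0.1 SD.
4. The quantities that match RQ2 and the stated purpose are P(ES <= 0) and P(ES <= -0.1).

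This step depends on no sample size, variance or prior.

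**Step 2: size, by illustration**

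Inputs:

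- N = 2,646 / 3 = 882. The one-third figure is in the v1.1 update. That 2,646 is the anticipated number, and that SDQ completion matches it, are assumptions.
- School share of variance 0.10, the figure in the sample size section. It is assumed to hold for the SDQ.
- R-squared of the YARC pre-test on the SDQ: not given, so varied from 0 to 0.40.
- Prior: the SAP gives "vague Gaussian priors (N(0,106) for each of the regression parameters"). It is centred at zero and is treated here as flat.

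The posterior of ES is taken as Normal(d, SE), with SE = sqrt(4 x (1 - R2) x (1 - 0.10) / N):

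- R2 = 0: SE = sqrt(3.6 / 882) = 0.064
- R2 = 0.16: SE = sqrt(3.024 / 882) = 0.059
- R2 = 0.40: SE = sqrt(2.16 / 882) = 0.049

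For an estimated benefit of 0.10 SD fewer difficulties (d = -0.10):

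| R2 | P(ES >= 0), as written | P(ES >= 0.1), as written | P(ES <= 0), intended | P(ES <= -0.1), intended |
|---|---|---|---|---|
| 0 | 0.059 | 0.0009 | 0.941 | 0.50 |
| 0.16 | 0.044 | 0.0003 | 0.956 | 0.50 |
| 0.40 | 0.022 | below 0.0001 | 0.978 | 0.50 |

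For an estimated harm of the same size (d = +0.10), the written rule gives P(ES >= 0) = 0.94 to 0.98 and P(ES >= 0.1) = 0.50, the former described as a positive effect.

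**The case against.** Four points can be made for the SAP.

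**The purpose is clear.** The update says it seeks the probability of a positive effect, speaks of effectiveness, and RQ2 asks about improvement. Read for purpose, an effect size of at least 0.1 means a benefit of at least 0.1, and a careful analyst would flip the sign. This bears on what is likely to happen. It does not remove the conflict, because the numerical rule and the signed effect-size formula still disagree with that purpose for this outcome. Nor does the SAP say in words that a higher SDQ score is worse; that follows from the names of the scales and the unreversed sum.

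**The report would expose the error.** Effect sizes and credible intervals are to appear beside the probabilities, and substantive differences from the frequentist results are to be discussed. In the illustration with R2 = 0, a reader would see ES = -0.10 with an interval of -0.10 +/- 1.96 x 0.064, about -0.23 to 0.03, on a scale named for difficulties. At the zero threshold the written figure is simply the complement of the intended one. Only the 0.1 threshold gives a number that does not convert directly. This stands and limits the harm.

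**The analysis is exploratory.** The SAP keeps the frequentist results as the main ones. This also stands. A reader might infer that the secondary result of the trial would be reported backwards. The document does not support that: the frequentist SDQ estimate and interval, and the Bayesian SDQ estimate and interval, keep their correct sign and meaning.

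**The SDQ components may be outside its scope.** A reader might also infer that the internalising, externalising and prosocial models share the fault. The Design overview lists only total difficulties as the secondary measure, and the update does not say that the Bayesian analysis covers the components, so that extension is conditional.

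**Conclusion.** The point holds in a limited form. On the SAP's own definitions, the two Bayesian probabilities specified for SDQ total difficulties measure a failure to improve, or a worsening, while the text labels them as evidence of a positive effect. This is a stated rule that is wrong for one of the two outcomes to which it is applied, not merely a missing detail.

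The reversal itself needs only the definitions. Its illustrated size (about 0.02 to 0.06 reported where 0.94 to 0.98 is intended, and at most 0.001 where 0.50 is intended) rests on the assumed N, flat prior, school share and R-squared, and on an estimated effect of exactly -0.10.

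Because only two exploratory probabilities for a secondary outcome are affected, and the correctly signed estimates appear alongside, this is a correction to make before reporting. It is not a threat to the trial's main conclusions.

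**What to change.** Add a sentence to the v1.1 update stating the direction of benefit for each outcome:

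- **YARC:** keep P(ES >= 0) and P(ES >= 0.1).
- **SDQ total difficulties:** report P(ES <= 0) and P(ES <= -0.1). Alternatively, reverse-score the total before analysis, say so, and keep the >= thresholds.
- **SDQ components, only if the Bayesian analysis is extended to them:** treat internalising and externalising problems like total difficulties, and keep >= for the prosocial scale. A single sign change across all SDQ scores would be wrong.

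The cost is one sentence in the SAP and one sign in the code. No data, model or sample size changes.

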As there is just one primary outcome no adjustments for multiple comparisons will be applied.

The equation to be estimated is:

$$Y_{ijt} = \alpha + \beta_1 Treat_i + \beta_2 Y_{ijt-1} + \beta_3 \gamma_i + s_i + \varepsilon_{ij}$$

where i are pupils and j are schools, Y_{ijt} is the YARC post-test score, Y_{ijt-1} is the YARC pretest score, $Treat_i$ is our treatment indicator (a dummy variable where 1 represents being allocated to receive the intervention and 0 represents allocation to the control group, i.e. not receiving the intervention), γ_j is a dummy variable indicating randomisation batch, s_j represent school fixed effects and ε being an error term. Where pre-test scores are missing, these will be imputed using the principles set out in the missing data section. As stated above, 2,392 of the 2,646 pupils in the classes eligible for testing completed a pre-test (this can be missing, for example, where pupils were absent on the day of testing, where special educational needs meant the test wasn't suitable, and where it was not possible to return to the school to conduct

assessments in the time available⁴). All 2,646 pupils are being approached for post-testing in order to maximise the potential available sample (rather than restricting this to pupils who completed pre-tests only). Thus for some pupils with post-tests, pre-test scores will be missing.

As this is effectively a multi-site trial, school identifiers will be included as fixed effects. This is in line with the EEF Statistical Analysis Guidance for an efficacy trial.

The analysis will be conducted in Stata (version 15).

Secondary outcome analysis

The approach to the secondary outcome analysis will follow the same approach used for the primary outcome. We do not have a measure of the secondary outcome at baseline, but will include the YARC pre-test score as it is still expected that this should account for some of the variance. In all other respects the analysis will remain the same. Thus our equation to be estimated is:

$$YS_{ijt} = \alpha + \beta_1 Treat_i + \beta_2 Y_{ijt-1} + \beta_3 \gamma_j + s_j + \varepsilon_{ij}$$

where YS_{ijt} is the SDQ score, instead of the YARC post-test score (and all other elements are as defined above).

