We will conduct exploratory analysis that examines separately whether there is an impact of the intervention on each of the four YARC subscales administered at post-test: letter sound knowledge, early word recognition, sound isolation, and sound deletion. This will follow the same model specification for the primary outcome, and adjust for the total YARC pre-test score in each case.

Analyses in response to missing data are discussed further below.

Update v1.1: Due to the third national lockdown and associated disruption for schools as a result of Covid-19, the decision was taken to stop post-testing in January 2021. This has resulted in a smaller number of completed post-assessments (around a third of the anticipated number). The smaller than anticipated sample size available for analysis inevitably has implications for the ability of the originally proposed analysis to detect a statistically significant effect (more generally, there is of course wider debate around the use of p-values to judge statistical significance, see for example, the discussion in Nuzzo, 2014). Bayesian methods can be used as an alternative means of evaluating effectiveness and may, though not in all circumstances, offer benefits when working with smaller sample sizes (McNeish, 2016).

While we will carry out the original analysis using frequentist methods as documented in the original version of this SAP, we will also undertake an additional exploratory analysis using a Bayesian approach. This will provide exploratory evidence into the probability that the

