We will assess balance by calculating absolute standardised differences (Imbens & Rubin, 2015) between the treatment and control groups and these will be presented in the report. Differences of greater than 10% will be considered as indicative of imbalance. If imbalance is observed we will run an additional sensitivity analysis incorporating any variables on which imbalance is present as additional covariates into the primary outcome model.

Missing data

We will report the number of complete cases (those without missing data). We will consider separately missingness in outcome data at post-test and missingness at pre-test, and will report the distribution of missing observations by treatment arm.

In the event of greater than 5% missing data at either cluster⁶ or individual level we will conduct further investigation into the mechanisms of missingness.

Any multiple imputation undertaken in response to missing data will focus on the primary analysis model, in line with EEF guidance. The extent to which multiple imputation is appropriate depends on the missingness mechanism.

Missing post-test data

If more than 5% of outcome data (total YARC post-test score) is missing (that is, as a percentage of the randomised sample) we will investigate the extent to which baseline characteristics (at school and pupil level)⁷ are correlated with missingness, using logistic regression, where the dependent variable is a binary indicator for missingness. If this shows significant associations with any of the characteristics, we would conduct an additional analysis including those covariates in the primary analysis model to assess the robustness of the main results.

Missing pre-test data

Again, where more than 5% of data is missing (that is, as a percentage of the randomised sample) we will undertake further investigation into the nature of missingness. This will follow the same approach outlined above of a logistic regression to explore the extent to which observed baseline characteristics are correlated with missingness.

Multiple imputation

Where the analysis above shows significant associations with the included characteristics, and where missingness does not depend on unobserved characteristics, the missing data are considered to be missing at random (MAR), and in this case, proceeding with multiple

⁶ That is, if data are missing for 5% of clusters.

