⁷ The characteristics to be included in the model will be pupil age in months, gender, FSM status and pre-test score where available, and a school identifier.

imputation (MI) is appropriate (in practical terms we will proceed with MI if any significant associations with observed characteristics are established). This MI would use those variables shown to be significant in the logistic regression alongside an indicator of treatment arm and school, using ten imputations⁸. Where appropriate, MI will be explored for imputing both pretest and post-test data. We will then compare the estimated treatment effect based on the imputed data with that from the primary analysis.

If, however, missing data depend on unobserved variables, the missing observations are missing not at random (MNAR), and this cannot be resolved through MI. In this case we would conduct further sensitivity analysis exploring the robustness of the results to differing specifications, including complete case analysis only; exclusion of the pre-test from the model, and using null imputation to impute missing pre-test scores.

Compliance

We will construct a measure of compliance based on information on whether parents opted out⁹ of receiving the texts and information on delivery of text messages. Thus compliance is effectively determined at parent level (which is applied at pupil level in the analysis – in most cases this is effectively the same, except in the case of siblings). The delivery team will provide the evaluation team with information on which parents opted out of receiving text messages and when this occurred, as well as information on whether messages were successfully delivered. This will allow the evaluation team to construct a measure of compliance, which will take a value between 0 and 1, set proportionately according to the number of messages received as a proportion of total possible messages¹⁰ (thus a value of 1 represents a parent who received all possible messages, and a value of 0.5 would represent a parent who received half of all messages).

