We will use this information on compliance in conducting a Complier Average Causal Effect (CACE) analysis to estimate intervention effects on treated pupils. This will be conducted for the primary outcome only. An instrumental variable (IV) approach will be used. We will estimate the CACE using two stage least squares (2SLS) regression by estimating a (first stage) model of compliance, using the measure of compliance described above and group allocation as the IV. The predicted values from the first stage are then used in the estimation of a model of our outcome measure. As per EEF analysis guidance, results for the first stage will be reported alongside with the correlation between the instrument and the endogenous variable and results of a F test. This analysis will be conducted using the ivregress command in Stata, which allows the necessary adjustments to be made to standard errors in response to the clustered nature of the data.

Non-compliance will also be examined through the implementation and process evaluation.

_

⁸ We propose 10 imputations given previous research indicating that at least a reasonable number of imputations (defined as 5 or more) should be performed (Hayati Rezvan et al., 2015), and as traditionally between 2 and 10 imputations were considered sufficient (Rubin, 1987).

⁹ Note that for a small number of parents/pupils, while they did not actively opt-out, messages were stopped (for example on request of the school due to specific circumstances). For the purposes of compliance analysis this will be treated in the same manner as opt-out.

¹⁰ The total number of possible messages is the same for all parents; even though parents randomised within the first batch began receiving messages one week earlier, the total number of possible messages received over the course of the intervention is the same.

Intra-cluster correlations (ICCs)

We will estimate the ICCs for the pre-test and post-test at school-level using empty hierarchical linear models including school-level random effects as follows:

$$Y_{ij} = \beta_0 + \eta_j + \varepsilon_{ij}$$

where Y_{ij} is the pre- or post-test of individual i in school j, β_0 is a constant term, η_j is a school-level random effect and ε_{ij} is an individual-level idiosyncratic error term. The ICC estimate is recovered as follows:

$$ICC = \frac{var(\eta_j)}{var(\eta_j) + var(\varepsilon_{ij})}$$

Effect size calculation

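### Imputation predictors are chosen by whether they predict missingness, so the pre-test can be left out when post-tests are imputed and the post-test is not a listed predictor for pre-tests; the usual cost is precision

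*SAP*

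**What the plan says.** - **Selection rule** (SAP, Missing data, Multiple imputation): "This MI would use those variables shown to be significant in the logistic regression alongside an indicator of treatment arm and school". The regression in question models a missingness indicator, not the test score.
- **Candidates** (footnote 7): "The characteristics to be included in the model will be pupil age in months, gender, FSM status and pre-test score where available", plus a school identifier. For missing pre-tests the section describes a "logistic regression to explore the extent to which observed baseline characteristics are correlated with missingness". The post-test is therefore not screened.
- **Route into the primary model** (Primary outcome analysis): "Where pre-test scores are missing, these will be imputed using the principles set out in the missing data section". Imputed post-tests are used differently: the resulting estimate is only compared with the primary one.
- **Number of imputations** (footnote 8): "We propose 10 imputations given previous research indicating that at least a reasonable number of imputations (defined as 5 or more) should be performed". Nothing ties the number to the fraction missing.
- **Data obtained** (Additional analyses, update v1.1): completed post-tests were "around a third of the anticipated number". The version history lists only the Bayesian analysis as new in v1.1, so the ten imputations appear to predate the shortfall.

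**The concern.** An imputation model should contain at least every variable in the analysis model it serves. Predicting missingness is a different property from predicting the score, and selecting on the first can discard the variable that matters most for the second. If the pre-test is dropped, imputed post-tests carry no relation to it. The imputed data then contradict the model fitted to them, and the standard error grows.

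MI is very likely to be triggered. Both 5% thresholds are passed, and any one significant association is enough to proceed, so age alone could start an imputation that omits the pre-test. The check on a trial that lost most of its primary outcome could then be less reliable than the analysis it checks, and could make a sound result look fragile.

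**Working it through.** **Inputs from the SAP.** 2,646 pupils in tested classes; 2,392 with a pre-test; 109 schools; pre-test explains 40% of variance; school explains 10%; ten imputations; about a third of anticipated post-tests obtained. If the anticipated number is 2,646, about 882 were observed (two-thirds missing). If it is the 2,000 implied by 100 schools of 20, about 667 were observed (75% missing).

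**Assumptions for the simulations.** True effect 0.10, pre-test explaining 40% of within-school variance, school fixed effects, ten imputations. The SAP does not say how the loss is spread over schools, so both patterns are shown. The ten imputations rest on citations, so there is no calculation to reproduce.

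**1. Chance that the pre-test survives the screen.** The Wald statistic has mean ln(OR) × √(N p(1−p)), and √(2,392 × 2/3 × 1/3) = 23.06. For OR 1.10 per SD: 0.0953 × 23.06 = 2.20, and Φ(2.20 − 1.96) = 59%. The same formula gives 20% at OR 1.05 and 90% at OR 1.15. With no association it is 5%.

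**2. Precision when the pre-test is dropped.** Within-school variance is 0.90; after the pre-test it is 0.90 × 0.60 = 0.54. With SE = √(4σ²/n) and n = 882:
- pre-test used: √(4 × 0.54/882) = 0.0495
- pre-test not used: √(4 × 0.90/882) = 0.0639, ratio 1/√0.60 = 1.29

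Simulated standard errors:

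| Pattern of loss | Omitted | Included | Increase |
|---|---|---|---|
| Two-thirds missing in every school | 0.065 | 0.051 | 27% |
| Same, separate simulation | 0.070 | 0.054 | 30% |
| 46 schools tested at 80% | 0.060 | 0.051 | 18% |
| 41 schools tested at 90% | 0.056 | 0.051 | 10% |

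In the first pattern complete cases give 0.050. The pre-test slope there falls from 0.60 to about 0.60 × 1/3 = 0.20.

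**3. Bias in the treatment effect.** Where missingness acts alike in both arms, omission gave 0.094–0.101 for a true 0.10. Now let missingness depend on the pre-test by ±0.15 log-odds per SD, in opposite directions by arm. The mean pre-test among those observed shifts by about 0.15 × 0.667 = 0.10 SD per arm, so the arms differ by 0.20 SD. Multiplied by the slope of 0.60, the bias is 0.12. Simulation agrees: about −0.02 in one direction and 0.21 in the other without the pre-test, against 0.097–0.104 with it. Complete cases are also close to 0.10. With 46 schools tested at 80% the same arithmetic gives 2 × 0.15 × 0.20 × 0.60 = 0.036, or about 0.03 in simulation. A main-effects logistic screen is not built to find this pattern.

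**4. Pre-tests imputed without the post-test.** Missing: 254/2,646 = 9.6%. The slope becomes 0.60 × (1 − 0.096) = 0.54, as simulated. The treatment effect was the same with and without the post-test (0.106 and 0.105). The SE was 0.0565 against 0.0532, a ratio of 1.06.

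**5. Ten imputations.** Let L be the fraction of missing information. Relative efficiency is 1/(1 + L/m), and Monte Carlo error as a share of the SE is about √(L/m).
- L = 0.667, m = 10: efficiency 93.8%, SE inflated by 3.3%, Monte Carlo error 26% of the SE. Bringing this to 10% needs m = 0.667/0.01 = 67; at L = 0.75, m = 75.
- L = 0.11–0.28 (loss mostly of whole schools): Monte Carlo error at m = 10 is 10–17%, and the 10% target needs m = 11–28.

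Forty repeats on one simulated data set with two-thirds missing within schools gave effects from 0.042 to 0.116 at m = 10, and from 0.074 to 0.100 at m = 70.

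**The case against.** The strongest reply is that the headline result does not use imputed post-tests. They feed a comparison, while the primary model always adjusts for the pre-test. Additional analyses also include a model restricted to observed pre-tests and one without the pre-test, so an outlying MI estimate would stand beside results that do not share its defect. This is correct and limits the consequence.

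A reader might infer that the primary treatment effect is biased. The SAP does not support that. The only route into the primary model is pre-test imputation, which leaves the effect about unbiased. Bias in the post-test MI needs missingness that differs by arm in its relation to the pre-test. Parents were randomised within classes and testing was halted by a national lockdown, so nothing stated makes that likely. In the within-school case the pattern would also leave about a 0.20 SD pre-test difference in the analysed sample, above the plan's 10% imbalance flag. In the 46-school case the difference is only about 2 × 0.15 × 0.20 = 0.06 SD, below the flag, but the bias is then about 0.03.

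A reader might also take 27%, or a need for 70 or more imputations, as fixed figures. Both depend on losses being spread within every school. If whole schools were lost, both shrink. The efficiency loss from ten imputations is modest in any case; the weakness is repeatability, and the 10% Monte Carlo target is a reviewing convention.

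Finally, joint or chained imputation of both tests could bring each into the other's model. The SAP foresees imputing both but does not specify this, and its selection rule points the other way. The point stands as a badly fixed rule.

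**Conclusion.** The concern holds as a defect in the stated selection rule. As written, the pre-test may drop out of the post-test imputation, and the post-test is not a listed predictor for the pre-test. The expected harm is a less precise MI estimate: about 27–30% on the standard error if two-thirds are missing within every school, about 10–18% if the loss is mostly whole schools. Bias of about 0.03–0.12 arises only under arm-dependent missingness. The primary model is touched only through pre-test imputation, at about 6% on the standard error. Ten imputations are too few for a repeatable result if missing information is near two-thirds, and closer to adequate if whole schools were lost. These sizes rest on the SAP's assumed 40% and 10% variance shares and on reading the shortfall as about two-thirds of 2,646.

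**What to change.** In the Multiple imputation section:

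- State that the imputation model always contains every primary-model variable (post-test, pre-test, arm, school), whatever its significance for missingness. Use the logistic screen only to add auxiliaries (age in months, gender, FSM).
- Say how schools without post-tests are handled, since a fixed school indicator cannot be estimated there. Either impute post-tests only in schools with at least one observed post-test, or use a random school intercept.
- Replace the fixed ten with a number set from the observed fraction of missing information, about 70 if it is near two-thirds and fewer if the loss is mostly whole schools. Report the Monte Carlo error.

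The cost is a few lines of text and some computing time.
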